SOC	System Organ Class
SOP	Standard Operating Procedure
SUSAR	Suspected Unexpected Serious Adverse Event
TEAE	Treatment Emergent Adverse Event
US	United States
WHO	World Health Organization

Protocol Number: ALLIO10 - 0021
Version 3.0; 27 July 2022

INVESTIGATOR SIGNATURE PAGE

The signature below constitutes approval of this protocol and provides the necessary assurance that this study will be conducted at his/her investigational site according to all stipulations of the protocol including all statements of confidentiality and in accordance with International Conference on Harmonisation (ICH) Good Clinical Practice (GCP) and local regulatory requirements.

Print Name	[name], APRN, PI
Title	Principal Investigator
Address of Institution/ Site	South Florida Family Health and Research Centers, LLC. DBA: Lice Cleanique [name], USA
[contact]

INVESTIGATOR SIGNATURE

07/28/2022
DATE

1. Synopsis

Study Title	Treatment of infestation with Pediculus humanus capitis in the community using a leave-in spray: A prospective, randomised controlled study.
Protocol Number	ALLI010-0021
Development Phase	Post-marketing confirmatory
Type of Study	Safety and efficacy
Test Product	Vamousse Spray 'n' Go
Name of Active Ingredient	Natrum Muriaticum 2X (HPUS)
Route, Dose, & Regimen	
Route: Topical application
 
Dose: Spray treatment to completely saturate each section. Work through hair with a comb to ensure full coverage down to the scalp. Thoroughly saturate all hair and scalp.
 
Regimen: Allow hair to dry naturally. Leave treatment in for a minimum of 8 hours

Control Product	Nix Creme Rinse Lice Treatment
Name of Active Ingredient	1% Permethrin
Route, Dose, & Regimen	
Route: Topical application
 
Dose: Thoroughly wet the hair and scalp with the permethrin lotion. Be sure to cover the areas behind the ears and on the back of the neck also. Allow the lotion to remain in place for 10 minutes.
 
Regimen: Rinse the hair and scalp thoroughly and dry with a clean towel.

Sponsor	Alliance Pharmaceuticals Ltd. [name], United Kingdom
Study Objectives	
The primary objective of the study will explore whether treatment with Vamousse Spray 'n' Go is more effective in killing lice & eggs compared to a permethrin-based control product.
 
The secondary objective of the study is to demonstrate the safety and local tolerability of Vamousse Spray 'n' Go in children 2yo+.

Study Endpoints	
The primary efficacy endpoint is the proportion of subjects who are lice free (defined as no live lice, adults or nymphs) 14 days after treatment.
 
The secondary efficacy endpoint is the number and percentage of all subjects who are lice-free at Day 2.

Number of Subjects and Site	The planned overall sample size for this Open-Label Clinical Trial is approximately 58 subjects to be enrolled at clinical research center in the United States, specifically Miami, FL. The subjects will be evenly divided between the Spray 'N' Go treatment group and the permethrin control group (29 subjects in each).
Eligibility Criteria	Subjects who satisfy ALL the inclusion criteria and have NONE of the exclusion criteria may be enrolled in the study.
Inclusion criteria	
1. Subjects identified as having an active head lice infestation within the previous 7 days, who have received no treatment at study entry.2. Subjects must have an active head lice infestation defined as: At least 1 live lice (adults and/or nymphs) present on the scalp and/or hair, as determined by a trained evaluator.3. Subject is male or female.4. Subject is at least 2 years and older years of age at time of enrollment.5. Subject is in good general health based on medical history.6. Each subject must have an appropriately signed Informed Consent agreement. A caregiver must sign an Informed Consent agreement for children not old enough to do so. Children ages 6-17 years of age will be administered a child's Assent Form. (The caregiver of a subject must be willing to allow all household members to be screened for head lice. If other household members are found to have an active head lice infestation, they must be willing and able to participate in study or receive the Standard of Care rapid headlice and nit removal with over the counter headlice treatment performed on site.)7. Subject agrees not to use any other form of lice treatments (commercial, community-anecdotal, or mechanical/manual) while participating in the study.8. Subject agrees to not cut or chemically treat their hair while participating in the study.9. Subject agrees to follow all study instructions, including attending all follow-up appointments. 
Female subjects of childbearing potential must be willing to have a urine pregnancy test prior to inclusion in this study.

Exclusion criteria	
1. Subjects with infested household members do not agree to take part in the study or receive the Standard of Care treatment.2. History of irritation or sensitivity to Natrum Muriaticum 2X (HPUS) or Vamousse Spray 'n' Go components, pediculicides or hair care products.3. Presentation at the treatment site with visible skin/scalp condition(s) that are not attributable to head lice infestation, such as an erythema score and atopic dermatitis that is >2, blisters, vesicles which, in the opinion of the investigative personnel or medical monitor, will interfere with safety and/or efficacy evaluations.4. Children under two years old.5. Use of any chemical, physical or mechanical lice removal treatment in any subject following diagnosis.6. Treatment for head lice (Over the counter [OTC], home remedy and/or Prescription) in the last 7 days.7. Any condition or illness that, in the opinion of the investigator, may compromise the objective of the protocol.8. Females who are pregnant, nursing or planning a pregnancy which could include subjects. If a household has a pregnant female who has an active case of lice, the entire household is excluded from participation.9. Subject of child-bearing potential, and unwilling to use an adequate method of contraception for the duration of the study. Adequate methods of contraception include: abstinence, vasectomized partner, oral birth control pills, birth control injections or patches, Intra uterine devices, condoms with a spermicidal jelly or a diaphragm with spermicidal jelly, surgical sterilization. Subjects and/or their caregivers will be considered non-child-bearing if the following has occurred: full hysterectomy or bilateral oophorectomy is considered surgically sterile. Tubal ligation is not considered equivalent to female sterilization.10. Participation in a previous investigational drug study within the past 30 days.11. Does not understand the requirements for study participation and/or may likely exhibit poor compliance, in the opinion of the investigator.12. Does not have a known household affiliation with their household members (i.e., do not stay in one household consistently, sleeping at one place several nights and then at another place or location). Household is defined as living in a shared area or space (for example the same house or apartment unit).
Withdrawal and Early Discontinuation	
A subject will be discontinued from this study if any of the following criteria are met:
 
• Withdrawal of consent by the subject is received.• In the opinion of the Investigator or Medical Monitor it is not in the subject's best interests to continue in the study.• Occurrence of an Adverse Event (AE) or Serious Adverse Event (SAE), which, in the opinion of the Investigator, warrants discontinuation of the subject from the study.

	
• Pregnancy as informed by the subject or as determined by a positive urine pregnancy test. If found to be positive, subject will be discontinued from the study.• The participant meets an exclusion criterion (either newly developed or not previously recognized) that precludes further study participation.• Head lice treatment product (over the counter [OTC], home remedy and/or Prescription): No medications are contraindicated for use with topical Natrum Muriaticum 2X (HPUS)
Medication/Products and Treatments	Vamousse Spray 'n' Go or Permethrin lotion
Study Product	Natrum Muriaticum 2X (HPUS) or 1% Permethrin lotion
Study Duration	14 Days +/- 3 Day window
Statistical Analysis	
ANALYSIS POPULATIONS
 
Safety Population includes all subjects receiving dispensed treatment. This is the population that will be used for the safety assessments.
 
Modified Intent-to-Treat (mITT) population includes all subjects who met all inclusion/exclusion criteria, were randomized, dispensed treatment, and had at least one post-treatment efficacy evaluation. This is the primary population for determination of the kill rate against head lice.
 
Per-Protocol (PP) population includes all subjects who received treatment, had no protocol deviations which could have interfered with the accurate assessment of treatment efficacy, and returned for the Day 14 visit within the allowed window. This population is the secondary analysis.
 
EFFICACY ANALYSIS
 
Primary Efficacy Endpoint The primary efficacy endpoint is the proportion of subjects who are lice free (defined as no live lice, adults or nymphs) 14 days after treatment.
 
Secondary Efficacy Endpoint The secondary efficacy endpoint is the number and percentage of all subjects who are lice-free at Day 2.
 
SAFETY ANALYSIS Descriptive statistics on the severity and duration of adverse events (AEs) from all subjects will be determined for any AE that occurs in at least 5% of the subjects.
 
Analysis of tolerability will be based on scores of Stinging/Burning and Itching sensations collected during Subject Self-Assessment and Source Document at all follow-up visits between the test and reference treatment groups.

PRINCIPAL CONTACTS	South Florida Family Health and Research Centers, LLC. DBA: Lice Cleanique [name], CEO [name] [contact] Mob.: [contact]

	[name], APRN, PI [name] [contact] [contact]
CLINICAL PROTOCOL AND CONDUCT INQUIRIES	Alliance Pharmaceuticals Ltd. [name] R&D Director [contact]
CLINICAL SAFETY INQUIRIES	Alliance Pharmaceuticals Ltd. [name] R&D Director [contact]
PROTOCOL DEVIATIONS	Alliance Pharmaceuticals Ltd. [name] R&D Director [contact]
IRB - Institutional Review Board:	Advarra IRB (Formerly Schulman IRB) [name] [contact] [contact]

2. Study Introduction

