2.3.2 Potential benefits

A demonstration of efficacy and safety with a single treatment application; spraying treatment completely saturate each section in showing safe to leave on overnight allowing hair to dry naturally with 8 hours exposure time. Vamousse Spray 'n' Go represents a significant addition to the current armamentarium for the treatment of head lice.

3. Objectives and Purpose

The study will explore whether treatment with Vamousse Spray 'n' Go is:

- more effective in killing lice & eggs compared to a permethrin-based control product.
- Clinically proven to kill lice & eggs, including super lice,
- Convenient to use - Spray 'n' Go can be left in the hair for the duration of the school day or overnight,
- works with one application or with re-application after 7 days if necessary,
- cosmetically acceptable/smells good/fast-drying,
- safe to use in children 2yo+

4. Study Design and Endpoints

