Day 14: The Investigator and medical staff will collect medical history, concomitant and prohibited medication review, perform vital signs, urine pregnancy testing if applicable, perform physical examination, record local application site reactions, ocular irritation assessment, perform a visual assessment for the presence of head lice (lice will be removed, counted, each stage examined and noted live or dead; 15 inch led 5x magnifying procedure lamp or laboratory microscopes are used for confirmation; nits will also be removed by clipping hair strands, examined, each stage counted, and noted as hatched or unhatched) and adverse events assessment. By day 14 if a subject reports clear signs of infestation (i.e., the presence of live lice) they will be regarded as a treatment failure and will be offered treatment with an alternative product (Vamousse Mousse) by clinical staff.

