4.2.2 Primary Endpoint

The proportions of participants in each of the study groups (i.e., treatment and control) who are completely free of live adult lice and nymphs at day 14

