4.2.3 Secondary Endpoints

- Assessment of infestations detected: number of live adult and nymph forms at the 7-day visit confirmed by investigator inspection during detection combing.
- Proportion of subjects requiring re-treatment at 7 days.
- Proportion lice free at day 2 (i.e., 24 hours after first treatment)
- Volume of product used in relation to hair type (Volume will be weighted pre and post and weight will be recorded on the product log. Hair type will be recorded as fine, medium or coarse on source document.)
- Safety of the product – as determined by reported adverse events during the study and recalled at the end of the treatment period.
- Cosmetic acceptability of the product in daily use as determined by consumer assessment questionnaire at the 14-day visit.
- The mean change between day 14 and baseline in the counts of live lice (i.e., total of live adult lice and nymphs) in each study group (i.e., treatment and control).

5. Study Enrollment and Withdrawal

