10.1 Statistical analysis plans

Treatment and control groups will be compared at the primary and secondary endpoints using the proportion of subjects in each group who are lice-free (i.e., no adults or nymphs) as the dependent outcome measure. The proportions for the two groups will be compared using the Z test for independent proportions. In either analysis if the numbers of subjects in the no lice category of either group is less than 10, an alternative estimate of the standard error will be used (e.g., Fisher's Exact or bootstrapping).

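### The objectives claim killing of lice and eggs, but no endpoint, hypothesis or between-arm test uses eggs, and Day 14 lice freedom cannot isolate egg kill

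*Combined protocol and SAP*

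**What the plan says.** **Objectives.** The Synopsis says the study will explore whether the spray "is more effective in killing lice & eggs compared to a permethrin-based control product". Section 3 (Objectives and Purpose) repeats this and adds "Clinically proven to kill lice & eggs, including super lice".

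**Endpoints.** The Synopsis defines the primary endpoint as "the proportion of subjects who are lice free (defined as no live lice, adults or nymphs) 14 days after treatment". Section 4.2.2 gives the same measure: participants "who are completely free of live adult lice and nymphs at day 14". The efficacy items in Section 4.2.3 include "number of live adult and nymph forms at the 7-day visit confirmed by investigator inspection during detection combing" and "Proportion of subjects requiring re-treatment at 7 days".

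**Analysis.** Section 10.1 compares the arms using the "proportion of subjects in each group who are lice-free (i.e., no adults or nymphs) as the dependent outcome measure". Section 10.4.2 adds a t-test on the change in live lice counts.

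**Egg data.** Section 4.1 has nits counted with stages noted at baseline and marked hatched or unhatched at Days 2 and 7. At Day 14, "nits will also be removed by clipping hair strands, examined, each stage counted, and noted as hatched or unhatched".

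**Re-treatment.** Sections 4.1 and 7.3.3 give a repeat application at Day 7 if live lice are present, and 7.3.3 adds thorough combing. Section 5.5.1 (item 5) instead treats a subject with live lice at a revisit as a failure and ends participation.

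**The concern.** Half of the stated primary objective has no measure attached to it. A significant Day 14 difference would formally satisfy an objective worded to include eggs, although no analysis had examined eggs. The Synopsis calls the study post-marketing confirmatory, and Section 3 uses the language of a product claim, so the objective's wording matters for what may be concluded.

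One defence would be that absence of nymphs at Day 14 shows the eggs were killed. The Day 7 re-treatment weakens that inference, because nymphs that hatch by Day 7 can be killed by the second application or combed out before the primary assessment.

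**Working it through.** **1. The plan's own figure, and what it powers.** Inputs from Section 10.5: lice-free rates 0.45 and 0.85, two-sided alpha 0.05, power 0.80, allocation 1:1. The mean rate is 0.65.

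- Without continuity correction: n = [1.960·√(2·0.65·0.35) + 0.842·√(0.45·0.55 + 0.85·0.15)]² / 0.40² = (1.322 + 0.515)² / 0.16 = 21.1, so 22 per group.
- With continuity correction: n = (21.1/4)·[1 + √(1 + 4/(21.1·0.40))]² = 25.9, so 26 per group, which matches the plan.
- Dropout: 26/0.90 = 28.9, so 29 per group, 58 in total.

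Both input rates are lice-free rates. The documents give no egg mortality or hatch rate for either product, so no sample size for an egg comparison can be computed.

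**2. Each measure against the egg part of the objective.**

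| Place | Variable | Eggs? |
|---|---|---|
| 4.2.2 primary endpoint | No live adults or nymphs, Day 14 | No |
| 4.2.3, three of seven items | Live counts at Day 7; lice free at Day 2; change in live count to Day 14 | No |
| 4.2.3, one item | Proportion re-treated at Day 7 | No (triggered by live lice) |
| 4.2.3, three items | Product volume, safety, cosmetic acceptability | No (not efficacy) |
| 10.3, four hypotheses | Lice-free proportion and change in live count, Days 14 and 7 | No |
| 10.1 and 10.4.2 tests | Z test on lice-free proportions; t-test on live counts | No |

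**3. Can Day 14 lice freedom stand in for egg kill?** Let f be the proportion with live lice at Day 7 and r the proportion of those cleared by re-treatment and combing. Suppose no egg is killed, every viable egg has hatched by Day 7, and subjects clear at Day 7 stay clear. Then

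Day 14 lice-free proportion = (1 − f) + f·r.

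| f (assumed) | r = 0.80 (assumed) | r = 0.95 (assumed) |
|---|---|---|
| 0.50 | 0.900 | 0.975 |
| 0.88 | 0.824 | 0.956 |
| 1.00 | 0.800 | 0.950 |

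At f = 0.88, the planned 0.85 is reached when r = (0.85 − 0.12)/0.88 = 0.83. A product with no effect on eggs could therefore succeed on the primary endpoint. This is an extreme case. The documents give no hatching time, and eggs hatching after Day 7 would lower these figures.

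**4. Do the Day 7 measures fill the gap?** Day 7 lice-free status, Day 7 counts and the re-treatment proportion are read at the visit where re-treatment is decided, so they carry some signal. But a subject infested at Day 7 may have lice that survived, eggs that hatched, or a re-infestation. No planned analysis separates these.

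**5. Could the nit records support a test?** Hatched status is not specified at baseline. At Days 2 and 7 nits are examined in place, and counting is explicit only at baseline and Day 14, so a Day 7 denominator is undefined. Combing falls inside the interval (after wash-out in Sections 6.1.8 and 7.3.1, and at Visit 2 in the schedule of events). Section 4.1 describes combing for the spray arm but not for the control arm, whereas 7.3.1 gives it to every subject. An unhatched nit may also still be viable.

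**The case against.** The strongest reply is that the objective only says the study will explore the question, and that endpoints, hypotheses, tests and sample size all agree on live lice. That is true, and it means neither the primary comparison nor its size changes. But an exploratory objective still needs a measure, and eggs have none.

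Several stronger readings are tempting, but the documents do not support them:

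- *Re-treatment makes Day 14 lice freedom uninformative about eggs.* Subjects clear at Day 7 are not re-treated, and eggs hatching later could still show at Day 14. The endpoint is confounded, not empty.
- *Every secondary endpoint is a lice count.* Section 4.2.3 also lists re-treatment, volume, safety and cosmetic acceptability. The accurate statement is that none uses eggs.
- *The nit data are discarded.* The introduction to Section 10 promises descriptive summaries and listings of all data collected. What is missing is a prespecified endpoint or comparison.
- *The pilot measures egg survival.* Section 10.5 reports 88% lice free on Day 0 and 12% at Day 14 after one application, a fall of 88 − 12 = 76 points. The pilot figures include no egg data, and re-infestation would fit equally well.
- *A nit-hatching endpoint could simply be tested with existing data.* Step 5 of the working shows why not.

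**Conclusion.** The mismatch holds on the text. The objective in the Synopsis and two bullets in Section 3 include eggs. The primary endpoint, the seven listed secondary endpoints, the four hypotheses and both tests do not. Day 14 lice freedom cannot isolate egg kill, and the Day 7 measures give only an indirect signal.

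The effect is on what may be concluded, not on the validity of the lice-free comparison; the 26 per group is untouched. The 80% to 97.5% range shows that success without egg kill is possible. It is not a forecast, and it rests on the assumed f and r and on the assumption that all viable eggs hatch by Day 7.

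The confounding argument also depends on the Day 7 re-treatment rule, which Section 10.5 relies on and Section 5.5.1 contradicts. Neither reading of that conflict creates an egg endpoint, so the mismatch between objective and analysis stands either way.

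**What to change.** 1. Delete '& eggs' from the primary objective in the Synopsis and from both Section 3 bullets that contain it.
2. State in Section 10 that the efficacy conclusion is limited to live adults and nymphs.
3. If nit data are reported, summarise them descriptively by arm. Note that unhatched nits may be viable and that combing may remove nits. State that these summaries do not support an egg-kill claim.
4. Reconcile Section 5.5.1 (item 5) with the Day 7 re-treatment rule in Sections 4.1 and 7.3.3.

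Items 1 to 3 need wording and a little analysis time, with no added subjects, visits or procedures. The downside is a narrower primary claim.

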At day 7, if live lice are still present, a repeat treatment will be administered. After day 7 if a subject reports clear signs of infestation (i.e., the presence of live lice), they will be regarded as a treatment failure and they will be offered treatment with an alternative product (viz., Vamousse Mousse) by clinical staff.

For the treatment group, Clinical staff will apply Vamousse Spray 'n' Go to fully coat dry hair and scalp, avoiding the eyes and mucus membranes. The Treatment will be left on the hair and scalp for 8 hours, then standard at home shampoo and rinsed off with warm water, followed by combing. The Treatment spray bottle is intended for a single use although it contains a sufficient quantity for two treatments. All household members will be instructed on an overall lice management program, which includes:

- Wash (in hot water) or dry-clean all recently worn clothing, hats, used bedding and towels.
- Wash (in hot water) personal care items such as combs, brushes and hair clips.
- Record time and date product shampoo/rinse 8 hours post treatment

For the control group, Clinical staff will first shampoo the hair and scalp using regular shampoo. They will then

thoroughly rinse and towel dry the hair and scalp, and allow hair to air dry for a few minutes. Shaking the permethrin lotion well before applying, they will proceed to thoroughly wet the hair and scalp with the permethrin lotion, being sure also to cover the areas behind the ears and on the back of the neck. After allowing the lotion to remain in place for 10 minutes, they will then rinse the hair and scalp thoroughly and dry with a clean towel.

The site will provide Subject with lice management instructions. Subjects will return for post-baseline visits assessments at Day 2, Day 7, and Day 14.

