5.5 Subject withdrawal and termination

5.5.1 Potential reasons for withdrawal

In accordance with the Declaration of Helsinki and other applicable regulations, a subject has the right to withdraw from the study at any time and for any reason without prejudice to his or her future medical care. The Investigator or Medical Monitor may also withdraw the subject at any time if it is medically necessary or in the interest of subject safety.

A subject will be discontinued from this study if any of the following criteria are met:

1. Withdrawal of consent by the subject is received. In the opinion of the Investigator or Medical Monitor it is not in the subject's best interests to continue in the study.
2. Occurrence of an Adverse Event (AE) or Serious Adverse Event (SAE), which, in the opinion of the Investigator, warrants discontinuation of the subject from the study.
3. Pregnancy as informed by the subject or as determined by a positive urine pregnancy test.
4. Significant non-compliance with study procedures that would interfere with the study results or increase the subject's risks in the study, as determined by the Investigator.
5. Subject is deemed to be a treatment failure if upon revisit it is determined that they are still infested having live lice. They will be terminated from the study and provided the standard of care at that point in the study.
6. Any clinical adverse event (AE), laboratory abnormality, or other medical condition or situation occurs such that continued participation in the study would not be in the best interest of the participant.
7. The participant meets an exclusion criterion (either newly developed or not previously recognized) that precludes further study participation.

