10.2 Data sets to be evaluated

The subject populations are defined as follows:

Safety Population includes all subjects who were administered treatment. This is the population that will be used for the safety assessments.

Modified Intent-to-Treat (mITT) population includes all subjects who met all inclusion/exclusion criteria, were randomized, administered treatment, and had at least one post-treatment efficacy evaluation. This is the primary population for determination of the effectiveness of the active treatment.

Per-Protocol (PP) population includes all mITT subjects who were administered treatment, had no protocol deviations which could have interfered with the accurate assessment of treatment efficacy, and returned for the Day 14 visit within the allowed window. This is the primary population for the efficacy comparisons between the two active treatment groups.

Subjects whose condition worsens and require alternate or supplemental therapy for the treatment of head lice during the study will be discontinued, included in both the mITT and PP population analyses as treatment failures. Subjects who discontinue early for reasons other than treatment failure will be excluded from the PP population, but included in the mITT population, using Last Observation Carried Forward (LOCF).

Efficacy analyses will be performed on both the per-protocol population and the mITT population. Safety analyses will be performed using the Safety population as defined.

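### The PP definition requires an in-window Day 14 visit, yet Section 10.2 also keeps some subjects discontinued earlier in PP as failures; read literally, the definition drops known failures and inflates PP lice-free rates

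*Combined protocol and SAP*

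**What the plan says.** **Synopsis, Analysis Populations.** PP covers treated subjects with no deviation that could affect the efficacy assessment "and returned for the Day 14 visit within the allowed window". There is no exception for subjects who failed earlier. On the role of PP: "This population is the secondary analysis". The mITT set is primary.

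**Section 10.2, PP definition.** It carries the same condition, "returned for the Day 14 visit within the allowed window", and gives PP a different role: "This is the primary population for the efficacy comparisons between the two active treatment groups".

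**Section 10.2, following paragraph.** Subjects whose condition worsens and who need alternate or supplemental lice therapy "will be discontinued, included in both the mITT and PP population analyses as treatment failures". Then: "Subjects who discontinue early for reasons other than treatment failure will be excluded from the PP population".

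**How a subject can fail before Day 14.** Section 4.1 says that subjects who report live lice after Day 7 are failures: "they will be regarded as a treatment failure and they will be offered treatment with an alternative product". Section 5.5.1, item 5, deals with subjects found at a revisit to have live lice: "They will be terminated from the study and provided the standard of care at that point in the study". Sections 4.1 and 7.3.3, by contrast, give a repeat treatment when live lice are present at Day 7, and 7.3.3 then schedules the final visit.

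**The concern.** A subject discontinued as a failure before Day 14 has no Day 14 visit. The definition sentence, in both places, leaves that subject out of PP. The later paragraph of 10.2 puts a subject who worsened and needed other therapy into PP as a failure. Every subject in dispute is a failure, so the choice between the two readings is a choice about whether known failures stay in the denominator.

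If they are dropped, the PP rate becomes success among those not already discontinued as failures. PP membership then depends on the outcome. The trial is open label, so a rule left unsettled until the data are in could be settled with the results in view. The stakes depend on the role of PP, on which the synopsis and 10.2 disagree.

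**Working it through.** **Inputs.** From Section 10.5: lice-free rates 0.45 (control) and 0.85 (treatment), two-sided alpha 0.05, power 0.80, 26 per group, and a pilot Day 14 rate of 12% after a single application. Assumed, because the documents do not give it: f, the share of an arm's failures discontinued before the Day 14 visit.

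**The plan's own figure.** Mean rate (0.45 + 0.85)/2 = 0.65.
- Uncorrected n per group = [1.96·√(2·0.65·0.35) + 0.8416·√(0.45·0.55 + 0.85·0.15)]² / 0.40² = 21.1, so 22.
- With continuity correction: (21.1/4)·[1 + √(1 + 4/(21.1·0.40))]² = 25.9, so 26 per group and 52 in total.

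The stated 52 reproduces with the continuity correction, and 26/0.9 gives 29 per group. The sample size is not in dispute here.

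**Effect of dropping early failures.** With true rate p, the PP rate is p / [1 − (1 − p)f]. The remaining numbers are 26(1 − 0.15f) on treatment and 26(1 − 0.55f) on control, rounded. Power is by exact binomial enumeration of the pooled two-sided Z test.

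Example, f = 0.25: treatment 0.85/(1 − 0.15·0.25) = 0.883; control 0.45/(1 − 0.55·0.25) = 0.522; difference 36.1 points.

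| f, equal in both arms | Treatment | Control | Difference (points) | n remaining | Exact power |
|---|---|---|---|---|---|
| 0 (failures kept) | 85.0% | 45.0% | 40.0 | 26 / 26 | 89% |
| 0.10 | 86.3% | 47.6% | 38.7 | 26 / 25 | 87% |
| 0.25 | 88.3% | 52.2% | 36.1 | 25 / 22 | 81% |
| 0.50 | 91.9% | 62.1% | 29.8 | 24 / 19 | 66% |
| 0.75 | 95.8% | 76.6% | 19.2 | 23 / 15 | 47% |

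**Is the direction fixed?** No.
- Unequal shares: f = 0.50 on treatment and 0 on control gives 91.9% v 45.0%, a gap of 46.9 points, wider than 40. The break-even treatment share is 0.20 when the control share is 0.10, and 0.52 when it is 0.25, so roughly twice the control share.
- Rates near the pilot: at 12% on treatment against 45% on control, the gap in favour of control is 33.0 points with failures kept. At f = 0.50 the rates are 0.12/(1 − 0.88·0.50) = 21.4% and 62.1%, a gap of 40.6 points before rounding.

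What does not depend on these assumptions is that the PP rate rises in any arm that loses failures, provided that arm has some successes.

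**The case against.** **The intent of 10.2 is clear.** Read whole, 10.2 excludes early discontinuations only when the reason is something other than treatment failure, and it says outright that subjects discontinued for other therapy count as PP failures. On that view the later paragraph qualifies the definition, and the synopsis merely omits a detail. This largely stands as a reading of intent. It does not settle the matter. The definition sentence in 10.2 itself carries the unqualified Day 14 condition. The exception names subjects who worsen and need other therapy, not every early failure.

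**Neither section, taken alone, harms its own primary comparison.** Where the synopsis would drop failures, PP is secondary. Where 10.2 makes PP primary for the comparison between arms, failures are kept. This stands. The main comparison is affected only if the literal definition is combined with 10.2's role for PP.

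**The number affected may be small.** No visit is scheduled between Day 7 and Day 14. If subjects with live lice at Day 7 are re-treated and continue, only failures reported between visits leave early. Subjects first found with live lice at an in-window Day 14 visit stay in PP under either text. This also stands. A large f would need the termination rule in 5.5.1, which conflicts with the re-treatment text.

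**A stronger reading to avoid.** A reader might infer that dropping early failures necessarily makes the arms look more alike. That holds at the planning rates when the early-failure shares are similar. The documents do not fix those shares, and the calculations above show cases where the gap widens.

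**Conclusion.** The contradiction is real, and it sits inside Section 10.2 as well as between 10.2 and the synopsis. Taken literally, the PP definition removes subjects discontinued as failures before Day 14 and inflates the PP lice-free rate in any arm where that occurs.

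At the planning rates with equal shares, the loss is modest for small f (1.3 points of difference and about 2 points of power at f = 0.10) and material for large f (10.2 points of difference and about 23 points of power at f = 0.50). These sizes rest on an assumed f and on 85% v 45% being true. The direction of the effect on the gap is not certain. Because mITT is also analysed and 10.2 shows an intent to keep failures, this is a definition to align before the data are seen. It does not show that the planned main comparison is biased.

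**What to change.** Put one PP definition in the synopsis and in Section 10.2, for example: *PP comprises mITT subjects without any deviation liable to distort the efficacy assessment who either attended Day 14 in window or had already been discontinued from the study as a treatment failure; the latter count as not lice free at Day 14.*

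The condition should be discontinuation as a failure, and not merely having been declared one. Given Section 5.5.1, item 5, the looser wording could score as a failure a subject who was re-treated at Day 7 and is lice free at Day 14.

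Also:
- State one role for PP, the same in the synopsis and in 10.2.
- Reconcile the passages on live lice at a revisit (Sections 4.1, 5.5.1 item 5 and 7.3.3), since they determine who leaves early.
- Reconcile the Day 14 window, which determines PP membership: ±3 days in the synopsis (given for study duration), +2 days in 7.3.3 and ±2 days in 7.3.4.

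The definition itself costs one sentence in each of two places and needs no new data. Reported PP lice-free rates may be somewhat lower than under the literal definition.
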